### ***3.1. Duration of Study***

Each subject will perform a pre-study evaluation, train using one of the protocols for three to twelve months, perform a post study evaluation as well as one and six month retention evaluations.

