## Home Based Virtual Rehabilitation for upper extremity

**Title of Project:**

**Principal Investigator:**

**[name] PT PhD**

**Funding Source(s):**

**NIDILRR #90RE5021-01-00**

**NIH NICHD #1R15HD095403-01A1**

### 1. Purpose/Specific Aims

The overarching aim of this study is to provide a mechanism for patients to engage in progressive motor practice for a meaningful time period. We aim to improve on the positive outcomes found in our work on patients in the chronic phase and the pilot work being done on patients in the acute in-patient phase post stroke to determine whether we can further improve functional recovery using a home based system.

Aim 1: Evaluate compliance with Home-Based Virtually Simulated hand/arm gaming activities and two computer game groups, one with motivation enhanced (ME) simulations and one with non-enhanced (MnE) versions, as compared to compliance with Standard hand/arm home Exercises (HBSE). Hypothesis: Participants in the ME and MnE group will show significant compliance as compared to the control group (HBSE) and the ME group will be superior to the MnE group.

Primary Outcome Measures: For the HBVS group, 1) time on task will be measured by the daily computer file time stamp and 2) amount of moving time will be measured by the actual movement time recorded by the games. For the computer games groups 1) time on task will be measured by recording start and stop time of practice in a notebook and 2) amount of moving time will be measured by commercially available activity monitors.

Aim 2: Evaluate the effectiveness of home-based virtually simulated hand/arm gaming activities (HBVS) for individuals with stroke as compared to a program of standard hand/arm home exercises (HBSE). Hypothesis: Participants completing HBVS training will exhibit significantly improved clinical, kinematic and neurophysiological outcomes as compared to the control group (HBSE).

Primary Outcome Measures for Aim 2: Wolf Motor Function Test, Upper Extremity Fugl-Meyer Assessment of Sensorimotor Recovery after Stroke, Action Research Arm Test, Perception of System Questionnaire, the Stroke Impact Scale, Kinematics, Cortical mapping.

Aim 3: Evaluate the impact of the motivation enhancements designed into computer games to provide a more enjoyable training experience. Hypothesis: Enjoyment of the games will be a more valid predictor of compliance than personal factors.

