### **5. Data Handling and Statistical Analysis**

All efforts will be made to keep subjects' personal information confidential. All subject names will be removed from the data and the data will be tagged using a coded ID number.

Demographic, clinical outcome and survey data will first be recorded on paper. All kinematic and computerized performance data will be collected on computer. These computer files will be identified by the coded subject ID number. All data will be transferred to an Excel spreadsheet with subjects identified by this same ID number. Spreadsheets will be stored on a drive that is password protected. Data will only be accessible to study staff and will be retained for seven years. The link between subject identity and subject ID number will be destroyed when data collection is completed.

Our primary outcome measures will be the WMFT (Aim 2) and the duration of motor activity (measure of compliance, Aim 1). The primary outcome measures and all secondary outcome measures described above will be subjected to a repeated measured analysis of variance, with between-group factors Therapy Type (Virtual Simulations (VS), Standard Exercise (SE)) and within-group factor Test (Before, Post, One Month retention, Six Months Retention). Our post-hoc analyses of the Therapy Type by Test interaction effects will focus on the Month 1 versus Month 6 comparison. We will be quantifying training effects by comparing group means as well as by percent change in performance, and by comparing the recovery curves obtained from Tests 1-4. All clinical outcomes used are well established measures of upper extremity functional recovery with published minimum clinically important differences which we will use to evaluate the significance of our findings.

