targeted to train movement of their shoulder, elbow and fingers. The physical therapist will set up the apparatus in their home and visit them once or twice in the first week to train them how to use the system and how to play the games. After this training period they will then continue to practice in their homes independently with on-line support from the therapist and in-person or on-line assistance from the study-engineer as needed. Both groups will be instructed to perform all three of the simulations assigned to them for at least twenty minutes, daily for twelve weeks.

**Figure 5.** Left: Patient home system setup with the passive arm support, hand tracking device and computer. Right: Patient is able to talk to and see therapist (lower left corner) and while playing games, patient's game screen is shared with therapist at the same time as well.

(career score) on that simulation, and the top ten career scores for the entire program (including other subjects). When users achieve a

The enhanced motivation (EM) group will train using three simulations (See Table 2). These simulations will all provide the user with eight to twelve levels of gradually increasing difficulty and complexity. There is a screen announcing each level change and the graphics for each new level change substantially. Scoring opportunities increase at each new level as well. When a simulation is completed, for the day, a leaderboard displays the user's score for the day, their total points scored for the entire training period

milestone career score (1 million points, two million points, three million points), they will have an opportunity to choose a new avatar for future play. This opportunity is provided at the beginning of gameplay.

The unenhanced control (UC) group will perform the same three simulations. Difficulty will increase utilizing an adaptive control algorithm that increases difficulty based on performance. Difficulty changes are extremely incremental making them imperceptible for most subjects. Graphics and scoring will not change as difficulty level changes. Total score for the day will be displayed after each simulation for the day is completed, but no leaderboard displaying past performances, career scores or the career scores of other subjects will be displayed. UC subjects will use the same avatars for the entire experiment.

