Hand opening/closing range of motion	Sum of maximum angular excursions of the paretic metacarpophalangeal (MCP), proximal inter-phalangeal (PIP) and distal inter-phalangeal joints (DIP) joints.
Hand opening velocity	Peak angular velocity during hand opening
Hand trace RMSE	Ability to control hand opening as subject moves a cursor tracking a sine wave. Reported as root mean square error (RMSE) comparing target position and cursor position.
Wrist Trace RMSE	Ability to control wrist flexion and extension as subject moves a cursor tracking a sine wave. Reported as root mean square error (RMSE) comparing target position and cursor position.
Horizontal shoulder and elbow trace RMSE	Ability to control shoulder and elbow as subject moves a cursor tracking a sine wave. Reported as root mean square error (RMSE) comparing target position and cursor position.

*Rationale:* Very few rehabilitation studies examine the interaction between motivation and adherence quantitatively. Utilizing knowledge of this interaction to inform design of rehabilitation simulations should advance the field of home based rehabilitation substantially.

*Hypothesis:* We predict that intrinsic motivation related to game play will predict adherence more effectively than patient readiness alone.

*Subjects:* The same subjects will be utilized for all three aims.

*Outcome measurements:* will include number of sessions as well as total intervention time and average session time. Time signatures from the telerehabilitation system will be used to overcome overestimation effects associated with patient self-reports of actual exercise time (59).

In an attempt to expand our understanding of the interaction between motivation (as measured by the IMI) and adherence to the autonomous home rehabilitation program, we will perform an in depth qualitative analysis focusing on subjects' unique perceptions and understandings of their participation in the proposed rehabilitation program. Using a Grounded Theory approach (60, 61), data collection and analysis will follow

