these steps: 1) A trained interviewer will ask open-ended questions in telephone interviews, allowing participants to reflect on and describe their experiences. 2) Investigators will read participants' narratives to develop a general sense of the subjects' experiences and attitudes toward the rehabilitation program. 3) Investigators will identify emerging narrative themes in participants' experiences and attitudes toward the program. 4) Finally, an iterative coding process will be used to refine initial findings and synthesize these themes.

*Statistical Analysis:* (See Table 5 for a summary of all planned comparisons.) Linear regression will be used to evaluate the effects of IMI (From Data Collection 1) on total time (Collected during training sessions).

**Aim 3: To test the impact of motivation enhanced, game-based interventions on the effectiveness of a telerehabilitation exercise program in persons with strokes.**

*Rationale:* Studies of clinic based interventions targeting hand function in persons with stroke have produced measurable changes in hand function that do not substantially reduce hand related disability. Study of a long term, home based program emphasizing adherence will inform the development of sustainable alternatives to costly clinic based interventions that fall short of the ultimate goal of rehabilitation.

*Hypothesis:* We predict that subjects in the ME group will demonstrate larger improvements in hand function as measured by the Action Research Arm Test (ARAT) than those performing UC interventions. We further predict that subjects in the ME group will demonstrate larger reductions in impairment and larger improvements in measures of motor control and quality of life than UC group subjects.

*Subjects:* The same subjects will be utilized for Aims 1-3.

*Outcome Measures:* (Please see Table 4 for the full listing and description of the proposed clinical and quality of life measures.) A trained RA, blinded to group assignment will collect all outcome measures described in Table 4 immediately prior to training, immediately after training and 3 months after training (Data Collections 1 and 2). The RA will be blinded to previous test scores during post testing and retention testing.

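### Training length is 3 to 12 months in the protocol but twelve weeks in the SAP; if it varies between subjects, total practice time reflects length as well as adherence

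*Protocol*

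**What the plan says.** **Length.** Protocol section 3.1 has each subject "train using one of the protocols for three to twelve months". It does not say who sets the length, when, by what rule, or whether it is balanced across arms. The SAP, under Treatment Protocol, instructs both groups to perform their three simulations "for at least twenty minutes, daily for twelve weeks".

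**Protocol outcome.** Section 5 names as a primary outcome "the duration of motor activity (measure of compliance, Aim 1"). For one group, section 1 says "time on task will be measured by the daily computer file time stamp", with moving time recorded by the games. No denominator or observation window is given, and the protocol does not say whether these times are summed over the training period.

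**SAP outcome.** The Aim 2 outcomes are "number of sessions as well as total intervention time and average session time". Table 4 gives a matching list: intervention days, total time and average time per intervention day. Only one adherence analysis is specified: "Linear regression will be used to evaluate the effects of IMI (From Data Collection 1) on total time (Collected during training sessions"). It has no term or offset for training length.

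**The concern.** Total time and session counts accumulate. A subject who trains for longer scores higher on both at the same daily adherence. If length differs between subjects, these outcomes mix how faithfully a person practised with how long the person was in training.

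Two analyses are exposed: the comparison of compliance between arms (protocol Aim 1) and the regression of total time on IMI (SAP Aim 2). The SAP plans for 30 subjects, so there is little precision to spare. If length were related to arm or to motivation, a difference in length could also be read as a difference in adherence or as an effect of motivation.

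**Working it through.** The plan states no figure for this point, so there is none to reproduce.

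**Inputs from the documents**
- Length: 3 to 12 months (protocol 3.1); twelve weeks, or 84 days (SAP, Treatment Protocol).
- Daily practice: at least 20 minutes (SAP). The protocol states no daily amount, so the twelve-month figure below applies the SAP's minimum to the protocol's upper limit.

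**Step 1. Practice time at full adherence** = minutes per day × days ÷ 60.
- Twelve weeks: 20 × 84 ÷ 60 = 28.0 h.
- Three months (365.25 ÷ 4 = 91.3 days): 30.4 h.
- Twelve months: 20 × 365.25 ÷ 60 = 121.75, about 122 h.
- Ratio of twelve months to twelve weeks: 365.25 ÷ 84 = 4.35. Within the protocol's own range it is 12 ÷ 3 = 4.

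The short end of the protocol range nearly matches the SAP (91.3 ÷ 84 = 1.09); the conflict lies in the rest of the range. A subject practising on 84 ÷ 365.25 = 23% of days for twelve months logs the same total as one with perfect adherence for twelve weeks. If the 20 minutes is meant for each of the three simulations, the hours triple (84 h and about 365 h) and the ratio does not change.

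**Step 2. Share of variance due to length (illustration).** Write total time as T = R × L, where R is the adherence rate and L the length, and assume that they are independent. With CV the coefficient of variation:

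share due to L = CV_L² ÷ (CV_L² + CV_R² + CV_L² × CV_R²)

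The documents give no distribution for either, so both are assumptions:
- L uniform over 3 to 12 months: CV_L = (9 ÷ √12) ÷ 7.5 = 0.346, CV_L² = 0.12.
- Half the subjects at 3 months and half at 12: CV_L = 4.5 ÷ 7.5 = 0.60, CV_L² = 0.36.

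| CV of adherence rate | Uniform 3–12 months | Half 3, half 12 | Fixed twelve weeks |
|---|---|---|---|
| 0.2 | 73% | 87% | 0% |
| 0.3 | 54% | 75% | 0% |
| 0.5 | 30% | 51% | 0% |
| 0.8 | 14% | 29% | 0% |

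Example, first cell: 0.12 ÷ (0.12 + 0.04 + 0.0048) = 0.728.

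**Step 3. Effect on the regression when length is unrelated to IMI.** If L is independent of both R and IMI, the correlation of IMI with total time equals its correlation with the rate multiplied by CV_R ÷ √(CV_L² + CV_R² + CV_L² × CV_R²). For uniform length this factor is 0.49, 0.64, 0.79 and 0.87 at the four CVs in the table. With a fixed length it is 1. This is added noise and not bias.

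**Step 4. When bias arises.** The arm comparison is biased only if length differs by arm, and the regression only if length is related to IMI. Neither document says that this happens. Neither prevents it, because neither requires the length to be fixed before randomisation.

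**The case against.** The strongest reply is that the difficulty comes from joining two documents. Total time, session counts and the IMI regression appear only in the SAP, and the SAP fixes twelve weeks for both groups; under that plan length explains none of the variance. This is correct. A reader might infer that the planned regression already measures training length in place of adherence, and the documents do not support that. What remains is that nothing says the SAP's length governs. The SAP may describe a narrower sub-study, but the text does not say so. Even then, the protocol's open range and its own compliance outcome would stand as written.

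Three further points stand in part.
- A reader might take the length to be assigned. Protocol 3.1 does not say this. If subjects choose how long to continue, length is itself partly adherence, and total time captures it properly. The plan has to say which applies.
- Average session time and average intervention-day time do not scale directly with length and are already listed. No analysis is specified for either.
- Assignment is randomised, so a reader who infers a biased arm comparison goes too far: variation unrelated to arm costs precision only.

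It might also be inferred that post-training tests would fall at damagingly different times since stroke. This adds little: the protocol admits subjects from six weeks after stroke and sets no upper limit, so that interval varies in any case.

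**Conclusion.** The contradiction on training length is plain and unreconciled. Its statistical consequence is conditional: it arises if length varies between subjects as protocol 3.1 allows, and for the protocol's duration of motor activity only if that is summed over training.

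In that case, totals at full adherence range from 28 h (twelve weeks) to about 122 h (twelve months), at the SAP's daily minimum. With length uniform over the protocol range and independent of adherence, length accounts for 73% down to 14% of the variance in total time as the CV of the adherence rate goes from 0.2 to 0.8. These shares rest on assumed distributions; no single value should be quoted as the effect. The loss is one of precision unless length is related to arm or to motivation. Bias is a possibility that the plan leaves open, and not something the documents show.

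**What to change.** 1. Reconcile protocol section 3.1 with the SAP's Treatment Protocol. The choice of length is the sponsor's. State who sets the length and, if it varies, that it is set before randomisation.
2. Then one of two alternatives applies:
   - **One length for all subjects.** Total time can stand. Dividing by a constant number of days would change neither the test nor the regression.
   - **Length still varies.** In the protocol's Aim 1 comparison and the SAP's Aim 2 regression, analyse minutes practised per prescribed day and the proportion of prescribed days practised, over the pre-set period. Alternatively, count practice over one common window for all subjects. The common window also avoids comparing rates over unequal periods if practice tails off with time.
3. In protocol section 5, state the period over which duration of motor activity is measured.

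The cost is wording, and where length varies a recorded number of prescribed days for each subject. Practice beyond the prescribed period or the common window would not be counted.

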### ***3.2 Study Sites***

Testing and initial training will take place in the Bergen Building of the Rutgers Biomedical and Health Sciences Campus in Newark. Home training will take place in subjects' homes.

### ***3.3 Sample Size Justification***

In this pilot study we will seek sufficient power to detect a clinically significant difference in the Wolf score changes in these two pre-planned, primary comparisons. To evaluate these effects of training, we will assume a power level of .8 and a significance level of 0.05. With presumed correlation among repeated measures of 0.1 and effect size of 0.3, we will need a sample size of 25 subjects in each of the three groups (HBVS, ME and MnE) to observe a significant effect for the first comparison (G\*Power, version 3.1.5). Although we will screen for patients with homogeneous impairments, by its nature stroke is an extremely variable condition. Due to possible subject attrition, we will use a total of 30 subjects in each of the two groups.

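### Protocol Section 3.3 promises power for two primary Wolf comparisons but defines neither, sizes only the first, and sets no rule for testing both

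*Protocol*

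**What the plan says.** Protocol Section 3.3 (Sample Size Justification) opens by promising "sufficient power to detect a clinically significant difference in the Wolf score changes in these two pre-planned, primary comparisons". The operating characteristics follow once, for both: "To evaluate these effects of training, we will assume a power level of .8 and a significance level of 0.05". The remaining inputs are given as "With presumed correlation among repeated measures of 0.1 and effect size of 0.3", and the result as "we will need a sample size of 25 subjects in each of the three groups (HBVS, ME and MnE", a number needed "to observe a significant effect for the first comparison". The paragraph closes with "Due to possible subject attrition, we will use a total of 30 subjects in each of the two groups".

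Nothing in Section 3.3, or elsewhere in the protocol, says what the first and second comparisons are. Section 5 plans a repeated-measures analysis of variance "with between-group factors Therapy Type (Virtual Simulations (VS), Standard Exercise (SE", that is, a factor with two levels. It states no order of testing, no division of the 0.05 and no other multiplicity rule.

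The SAP text available for this review describes a two-group study of 30 people with the Intrinsic Motivation Inventory as primary outcome. It mentions neither the Wolf test nor multiplicity. It refers to a Table 5 of planned comparisons that is not in that text, so nothing is inferred here from that table's content.

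**The concern.** Two problems follow from the same few sentences.

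First, a power statement made for two comparisons is backed by a calculation for one. If the second comparison turns out null, a reader could take it as evidence of no difference under 80% power, although no such power was calculated for it.

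Second, two comparisons are called primary, one level of 0.05 is given, and nothing says how they are to be combined. If each is tested at 0.05 and either may be claimed, the error rate for the pair is nearly double the stated level. Because the comparisons are not named, the choice of which contrasts count as primary also stays open until the data are in.

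**Working it through.** **Inputs.** From Protocol Section 3.3: power 0.8, significance level 0.05, effect size 0.3, correlation 0.1, 25 per group, 30 with attrition. Assumptions: the effect size is Cohen's f, the usual convention for analysis of variance in the named software, and the calculation used m = 2 measures. Section 3.3 states neither.

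**Step 1: reproduce the 25.** For the between-groups test in a repeated-measures analysis with k groups and N subjects in total:

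λ = f² × N × m / (1 + (m − 1) × ρ), with k − 1 and N − k degrees of freedom.

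With k = 2, N = 50, m = 2: λ = 0.09 × 50 × 2 / 1.1 = 8.18 on 1 and 48 degrees of freedom. Power is 80.0%, so the stated 25 per group is recovered exactly. The other variants tried at 0.05 (three groups, three or four measures, within-subject or interaction tests) need 10 to 21 per group with two or three groups, or 29 to 42 for a single group. The 25 therefore fits a calculation for one two-group contrast.

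**Step 2: what this implies for the second comparison.** Its power depends on inputs that the protocol does not give. Using the same formula, two groups and 0.05:

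| Assumed f, second comparison | 25 per group | 30 per group |
|---|---|---|
| 0.30 (the only value in the text) | 80.0% | 86.9% |
| 0.25 (assumption) | 64.6% | 72.8% |
| 0.20 (assumption) | 46.4% | 53.8% |

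The second comparison may have the promised power or may fall well short of it. The documents do not allow a choice between these rows.

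**Step 3: error rate for the pair, both tested at 0.05, no true effect.**

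- Independent tests: 1 − 0.95² = 9.75%.
- Correlation 0.5 (two contrasts sharing one arm, equal arm sizes), bivariate normal: 9.07%.
- Correlation 0.8: 7.8%.

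A simulation of three arms of 25, with pooled variance on 72 degrees of freedom, agrees:

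| Pair of comparisons | At least one false positive |
|---|---|
| Both game groups pooled vs standard exercise, and ME vs MnE (orthogonal) | 9.7% |
| ME vs standard exercise, and MnE vs standard exercise | 9.0% |
| ME vs standard exercise, and ME vs MnE | 8.9% |
| Any pair, second tested only if the first is significant | 5.0% |

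These pairs are illustrations. The protocol does not say which, if any, is meant.

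**Step 4: an alpha split as the alternative.** At 0.025 per comparison with the Step 1 inputs, power is 70.7% with 25 per group and 79.5% with 30. Reaching 80% takes 31 evaluable per group. The protocol's step from 25 to 30 implies attrition of 1 − 25/30 = 16.7%, so enrolment would be 31 / (25/30) = 37.2, rounded up to 38 per group.

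**The case against.** A reader might infer that the second comparison is underpowered. The documents do not support that. They give no effect size for it, and under the only inputs they do give, a second two-group contrast with 25 per group has the same 80.0% as the first. A lower figure needs either a smaller effect that the reader supplies or a different model. Changing the model affects the first comparison too: for pooled games (50) against exercise (25) at 0.6 SD (f = 0.3 with two groups), power is 68% on a final score and 44% on a change score with ρ = 0.1. Such figures say nothing about being second. The mismatch between the sizing model and the planned analysis is a separate matter.

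A reader might also take ME versus MnE to be the second Wolf comparison, since Section 1 predicts that "the ME group will be superior to the MnE group". That sentence belongs to Aim 1 and concerns compliance. The Wolf test belongs to Aim 2, which contrasts only HBVS with HBSE, and Section 5 has only two therapy levels. The identification is a guess.

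Other objections carry some weight. Testing both at 0.05 is an inference: one level is stated, with no testing or success rule. A reader could suppose that alpha had already been split, because a three-group between-groups test at 0.025 with two measures also gives 25 per group (80.6% power), but the text says 0.05. The 9-10% requires arm contrasts that are independent or share one arm. Two time-point contrasts, say, could be more strongly correlated and give less. Finally, Section 3.3 calls this a pilot, and strict family-error control in a pilot is open to debate. But the same section claims power for pre-planned primary comparisons at a fixed level, so saying what that level covers is a fair request.

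**Conclusion.** The point holds in this form: Section 3.3 claims power of 0.8 at 0.05 for two primary Wolf comparisons, while the 25 per group was computed for the first only. Neither comparison is defined, and power for the second is neither stated nor verifiable. It has not been shown to be too low.

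No order or adjustment appears in Sections 3.3 or 5 or in the SAP text available. If both are tested at 0.05, the family error is about 9-10% for arm contrasts that are independent or share one arm, and less under stronger correlation. This rests on reading the single 0.05 as applying to each test and on either result being claimable. The reproduction of 25 rests on f = 0.3 and two measures. The plan should be changed, but the change is to the text and not to the size of the trial.

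**What to change.** In this order:

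1. Reconcile the arms. Section 3.3 lists HBVS, ME and MnE as three groups, leaves out the HBSE control, and then refers to two groups. Section 5 has a two-level factor. The comparisons cannot be written down until these agree.
2. Name the two Wolf comparisons in Section 3.3 and use the same contrasts in Section 5.
3. Test them in fixed sequence at 0.05, the second only if the first is significant.
4. State that the 0.8 was computed for the first comparison only.
5. Give the second comparison its own assumed effect size and the power that results, or label it exploratory.

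The cost is a rewrite of Section 3.3 and of the factor definition in Section 5, with no added patients. The downside is that the second comparison cannot be claimed as confirmatory if the first fails. If the sponsor wants each comparison to stand alone, splitting alpha at 0.025 is possible, but under the Step 1 inputs it means enrolling 38 per group instead of 30.

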## **4. Study Variables**

### ***4.1 Independent Variables or Interventions***

The two **computer game groups, Motivation Enhanced (ME) and Motivation Non-Enhanced (MnE)** will use the NJIT- Home Virtual Rehabilitation System (HoVRS) to play a series of computer games developed to practice movement of the hand and fingers. Subjects will first come into our lab, perform pre-tests as well as a pre-intervention training session. Then a physical therapist and engineer will set up the apparatus in subject's home and will train them on how to use the system and play the games in their home during the first week. The physical therapist and engineer will be in contact with subjects throughout the training and will visit subjects' homes as needed if problems are encountered. Additionally, the system allows the therapist to remotely monitor each day's activity.

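### Section 3.3 gives two incompatible sample sizes (3 × 25 and 2 × 30), leaves the HBSE control out of its groups, and cannot be tied to the Section 5 analysis; approaching 300 people yields at most 60

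*Protocol*

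**What the plan says.** **Size.** Protocol Section 3.3 sets power at 0.8 and significance at 0.05. "With presumed correlation among repeated measures of 0.1 and effect size of 0.3", it concludes that "we will need a sample size of 25 subjects in each of the three groups (HBVS, ME and MnE", citing G\*Power. Two sentences later, allowing for attrition, it states that "we will use a total of 30 subjects in each of the two groups". Those two groups are not named.

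**Comparisons.** The stated target is "a clinically significant difference in the Wolf score changes in these two pre-planned, primary comparisons". Section 3.3 does not say what the two comparisons are, and the sample size is given only "to observe a significant effect for the first comparison".

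**Arms elsewhere.** The Aim 1 hypothesis in Section 1 is that "Participants in the ME and MnE group will show significant compliance as compared to the control group (HBSE", with ME also superior to MnE. The Aim 2 hypothesis is that "Participants completing HBVS training will exhibit significantly improved clinical, kinematic and neurophysiological outcomes as compared to the control group (HBSE". Section 4.1 describes "computer game groups, Motivation Enhanced (ME) and Motivation Non-Enhanced (MnE" and, under its software headings, a video home exercise group. Section 5 specifies a repeated-measures ANOVA with two therapy levels (virtual simulations, standard exercise) and four test times.

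**Recruitment.** Section 3.5.3 expects 15-20% of people to meet the inclusion criteria and on that basis plans to approach 300.

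**SAP.** The Subjects paragraph under Aim 1 plans 30 people in total. Both SAP groups (enhanced and unenhanced) play computer games, and there is no standard-exercise arm.

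**The concern.** An attrition allowance should raise the total. Here the total falls from 75 to 60 within one paragraph, because the number of groups changes from three to two. The list of groups used for the calculation also leaves out the control arm on which Aims 1 and 2 depend.

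A reader therefore cannot say how many people will be randomised, to which arms, or which test the 80% power belongs to. The recruitment figure is presented as following from the sample size, yet it covers only the smaller total, and that only at the top of the stated eligibility range.

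**Working it through.** **Inputs.** From Section 3.3: effect size 0.3, correlation 0.1, alpha 0.05, power 0.80, 25 per group in three groups, 30 per group in two. From Section 5: two groups, four tests. From Section 3.5.3: 300 approached, 15-20% eligible. Assumptions: 0.3 is Cohen's f (the usual G\*Power ANOVA input), and epsilon = 1 (sphericity) unless stated. Section 3.3 gives no epsilon, but a single common correlation with equal variances implies 1.

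**Step 1: totals.**
- Required: 3 × 25 = 75.
- Enrolled as written: 2 × 30 = 60, or 60/3 = 20 per arm if there are three arms.
- If three arms of 30 were meant: 3 × 30 = 90.
- Going from 25 to 30 implies a loss of 1 − 25/30 = 16.7%.

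**Step 2: arms, side by side.**

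| Place | Arms |
|---|---|
| Section 1, Aim 1 | HBVS activities and two game groups (ME, MnE), against HBSE |
| Section 1, Aim 2 | HBVS, HBSE |
| Section 3.3, requirement | HBVS, ME, MnE |
| Section 3.3, enrolment | two, unnamed |
| Section 4.1 | ME, MnE, video home exercise |
| Section 5 | virtual simulations, standard exercise |
| SAP | enhanced, unenhanced (30 in total) |

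The video home exercise group is read here as HBSE.

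**Step 3: reproduce 25.** Noncentral F, with k groups, m measurements and total N:
- Between-factor effect: λ = f²·N·m / (1 + (m−1)ρ), df = k−1 and N−k.
- Interaction: λ = ε·f²·N·m / (1−ρ), df = ε(k−1)(m−1) and ε(N−k)(m−1).

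For k = 2, m = 2, between-factor, N = 50: λ = 0.09 × 50 × 2 / 1.1 = 8.18, df 1 and 48, power 0.800. At 24 per group power is 0.783. So 25 is the minimum for that test.

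**Step 4: same inputs, other designs.** Minimum n per group for power of at least 0.80:

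| Design | Effect | n per group | Power |
|---|---|---|---|
| 2 groups × 2 tests | between | 25 | 0.800 |
| 2 × 4 (Section 5) | between (Therapy Type) | 16 | 0.821 |
| 2 × 4 (Section 5) | interaction, ε = 1 | 15 | 0.821 |
| 3 × 2 | between | 21 | 0.807 |
| 3 × 2 | interaction | 18 | 0.823 |
| 3 × 4 | between | 13 | 0.812 |
| 3 × 4 | interaction, ε = 1 | 13 | 0.835 |
| 3 × 2, alpha 0.025 | between | 25 | 0.806 |
| 2 × 4 | interaction, ε = 0.45 | 25 | 0.805 |

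The last two rows use values that Section 3.3 does not state, and they also give 25. The number alone therefore does not identify the test.

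**Step 5: power of the Section 5 ANOVA on the stated inputs** (two equal groups, ε = 1):

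| N | Interaction | Therapy Type main effect |
|---|---|---|
| 60 | 0.990 | 0.980 |
| 50 | 0.971 | 0.954 |
| 45 | 0.953 | 0.932 |
| 38 (45 × 25/30 = 37.5, rounded up) | 0.910 | 0.884 |

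**Step 6: recruitment.**
- Yield: 300 × 0.15 = 45; 300 × 0.20 = 60.
- To approach for 60: 60/0.20 = 300 to 60/0.15 = 400.
- For 75: 375 to 500. For 90: 450 to 600.

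All of these are before refusals.

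**The case against.** **It may be an editing slip.** The pattern 2 × 30 = 60 = 20% of 300, with 25 reproducing for two groups, suggests a two-arm plan only partly edited to three. HBVS in Section 3.3 may also be a slip for HBSE, which would match Section 4.1 exactly. Both are plausible, but both are inferences. Aim 1 can equally be read as four arms (4 × 25 = 100, or 120 with the same allowance). The text does not settle which reading is meant.

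**A reader might infer that 25 is a miscalculation, or that the wrong test was powered because a between-factor test averages Before with Post.** The documents do not support either. The protocol never names the between-factor test, and Step 4 shows other routes to 25.

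**A reader might infer that the trial is underpowered.** That is not shown. On the stated inputs the Section 5 ANOVA keeps 88% power or more even at 38 people. Lower figures need an epsilon that the protocol does not give: at N = 45, interaction power is 79% at ε = 0.5 and 67% at the floor of 1/3. The Step 5 figures also assume equal groups. If two game arms are pooled against one exercise arm (2:1, same mean difference), f becomes about 0.283 and interaction power at ε = 1 is 98% at N = 60 and 93% at N = 45. While the arms are unresolved, none of these is the trial's own power.

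**A reader might infer that recruitment must fail.** It meets the 60 written in Section 3.3 if 20% are eligible and nobody refuses. The 90 is not stated anywhere in the protocol and applies only if three arms of 30 are meant.

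**It is a pilot.** That is so, but Section 3.3 still claims 0.8 power for a clinically significant difference.

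**Conclusion.** The contradiction stands and needs no statistical assumption. Section 3.3 requires 75 and enrols 60, and its list of groups omits the HBSE comparator. Sections 1, 3.3, 4.1 and 5 do not agree on the arms. The yield of 45-60 from 300 people reaches 60 only in the best case and cannot reach 75.

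With 0.3 read as Cohen's f, alpha 0.05 and ε = 1, the Section 5 ANOVA needs 15-16 per group and the three-group designs in Step 4 need 13-21. The 25 therefore cannot be tied to the planned analysis. The harm is that the randomised number, the arms and the powered test are undefined. A loss of power in the planned analysis is not demonstrated.

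The SAP's 30 is not in itself an error, but its relation to the protocol total is not stated.

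**What to change.** 1. Give one list of randomised arms, including the standard-exercise control, with the same names in Sections 1, 3.3, 4.1 and 5. Say how ME and MnE map onto the two therapy levels in Section 5.
2. State one enrolment total. Say whether the SAP's 30 are part of it or a separate comparison.
3. Name the two primary comparisons, and say which one, and which effect (main effect or interaction), the n is for. Restate power for that test at the planned n and allocation, with any epsilon assumed and the Wolf difference and standard deviation behind the effect size.
4. Align the number approached with the total: 300-400 for 60, or 450-600 for 90, before refusals. Otherwise state expected enrolment as at most 45-60 with the power that gives.

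The cost is wording and recalculation. If the sponsor keeps the number it can recruit, the power and arms should be restated for that number rather than patients added. Only if three arms of 30 are confirmed does the total rise, to 90, which is 30 more than Section 3.3 now enrols.
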